8.1.8. Early Withdrawal Visit

Any participant who withdraws early or is discontinued for any reason will be asked to complete an EWV.

1. For participants in Groups 1 and 2, review the participant's remaining antibiotic supply and count the number of remaining doses to document compliance; record total remaining in source document.
2. Perform complete physical examination.
3. Assess vital signs (seated/semi-recumbent blood pressure, heart rate, respiratory rate and temperature).
4. For WOCBP, collect and perform serum pregnancy test.
5. If EWV occurs within the visit window for Day 37, collect blood sample for TNA.
6. Collect blood sample for hematology.
7. Collect blood sample for serum chemistry.
8. Collect urine sample for urinalysis.
9. For participants who have received at least one vaccination, collect blood sample for TSH & autoantibody determination.
10. Review entries in e-diary with participant.
11. Review and record AEs.
12. Record concomitant medications.

8.1.9. Unscheduled Visits

Unscheduled visits will occur when necessary, in the opinion of the PI or designee, to follow-up on an AE or abnormal laboratory test result between scheduled visits. Additionally, participants who report a potential autoimmune-related condition at any of the safety follow-up phone calls will be requested to return to the clinic for an unscheduled visit to provide a blood sample for TSH & autoantibody testing.

Unscheduled visits occurring before Day 51 will include a symptom-directed PE, measurement of vitals, AE (includes SAE/AESI) assessment inclusive of reviewing the status of ongoing AEs since the prior visit, updating of medication usage since the last visit, and (if applicable) review of e-diary data since the last visit.

Unscheduled visits occurring after Day 51 will include an AE/SAE/AESI assessment including blood draw for TSH and autoantibody testing (if medically indicated) and updating of

AV7909 Anthrax Vaccine

IND 014451

Protocol EBS.AVA.210, Version 3.0 (28 October 2019)

medication usage since the last visit/contact (only if AE/SAE/AESI-related). Other evaluations performed by the PI or designee during the unscheduled visit as part of the participant's medical care (eg, vital signs, symptom-directed PE, etc) and recommendations given to the participant (eg, referral to the participant's personal physician or specialist for further diagnosis and/or care, prescribed medications) will be documented in the participant's medical chart at the site. In the event of any referrals for further medical care, the PI or designee will follow up with the participant and/or personal physician/specialist to ensure the reporting of any SAEs or potential AESIs per the protocol (refer to [Section 9.7.2](#)).

8.2. Immunogenicity/Efficacy Assessments

For all participants, blood samples for the determination of TNA titers will be collected on Day 1 and Day 37 (± 1 d) (2 weeks after the last vaccination). Blood samples will be collected at the EWV only if it falls within the visit window for Day 37.

All immunogenicity laboratory samples will be evaluated using a TNA assay. Specific procedures related to collection, processing, storage, and shipment of the samples will be provided in a Laboratory Manual.

The TNA assay being used in this trial has been validated by Battelle Memorial Institute (Columbus, Ohio) under National Institute of Allergy and Infectious Diseases sponsorship. The assay measures the functional ability of antisera containing anti-PA antibodies to specifically protect cells against *B. anthracis* lethal toxin cytotoxicity {[Stinson et al, 2005](#); [Li et al., 2008](#)}. The TNA assay results will be reported as the reciprocal of a serum sample dilution that results in 50% neutralization of lethal toxin cytotoxicity (50% effective dilution; ED₅₀). To standardize assay results, the results are divided by the ED₅₀ of a serum reference standard, and the resulting ratio is reported as a 50% neutralization factor, NF₅₀. Reference standard AVR801 will be used.

8.3. Safety Assessments

8.3.1. Adverse Events

Refer to [Section 9, Reporting Adverse Events](#).

8.3.2. Clinical Laboratory Tests

All analytes to be tested during screening/safety/autoimmunity clinical laboratory tests are specified in [Table 10](#). Instructions for the collection, processing, storage, and shipment of screening and safety clinical laboratory test samples are provided separately in the Laboratory Manual. All samples will be sent to the central laboratory for analysis, except urine for pregnancy testing, which will be performed at the site and results documented in the eCRF.

It is the responsibility of the PI or designee to review the results of all screening and safety laboratory tests (including unscheduled lab tests) as they become available, initially for the assessment of study eligibility and subsequently for the continuous safety monitoring of participants. Review of the laboratory reports must be documented.

The following assessments will be performed at Screening only:

- Urine drug screen (refer to [Table 10](#) for analytes).

AV7909 Anthrax Vaccine

IND 014451

Protocol EBS.AVA.210, Version 3.0 (28 October 2019)

- Serologic testing (HIV-1/HIV-2 antibodies, HBV surface antigen, and HCV antibody). Confirmatory testing will be performed on any samples that test positive for either HIV or HCV; no additional blood/serum will be required for this confirmatory testing.
- FSH test in postmenopausal women; refer to [Section 5.1](#).

Pregnancy testing will be performed at Screening, immediately following group assignment, before each vaccination, and at the Day 51 Final Study Visit or at the EWV. Female participants who are surgically sterile or are confirmed at Screening to have an FSH level >30 mIU/mL (ie, postmenopausal; refer to [Section 5.1](#)) are exempt from pregnancy testing. A serum pregnancy test is required at Screening for all other female participants (ie, WOCBP). Post-screening pregnancy testing in all women not having an FSH level >30 mIU/mL (ie, WOCBP) will consist of a UPT at the above specified visits except for a serum pregnancy test performed at the (if applicable) EWV. All UPTs must be performed at the investigational site and documented to be negative prior to vaccine administration. For participants with positive UPT results, a confirmatory serum pregnancy test will be performed. IP will not be administered to any participant who tests positive for pregnancy. If group assignment occurs within four days of a negative Screening serum pregnancy test, a UPT does not have to be performed.

Blood and urine samples for safety clinical laboratory testing (hematology, serum chemistry, urinalysis) will be collected at Screening and Day 51 as well as at the EWV if the EWV occurs before Day 51. Refer to [Table 10](#) for the list of analytes for hematology, serum chemistry and urinalyses. The laboratory test results will be evaluated against the FDA toxicity grading scale provided in [Table 13](#) of [Appendix A](#).

In addition, blood samples for TSH & autoantibody assessment of ANA, RF and anti-dsDNA will be taken at Day 1 after randomization, Day 51 or EWV or an unscheduled visit if the participant has received at least one dose of vaccine and at the time of safety follow-up phone contact(s) if warranted from participant report(s) of a potential AESI (see [Table 10](#) for the list of analytes for autoantibody testing). These samples will be shipped to the central laboratory and will be banked; testing for TSH and ANA, RF and anti-dsDNA autoantibodies will be performed only if medically indicated (as per PI's discretion based on a report of a potential AESI).

Instructions for the collection, processing, storage, and shipment of laboratory samples will be provided separately in the Laboratory Manual.

It is the PI's responsibility to review the results of all screening and safety laboratory tests (including unscheduled lab tests) as they become available, initially for the assessment of study eligibility and subsequently for the safety monitoring of participants. Review of the laboratory report must be documented.

For each abnormal laboratory test result, the PI needs to ascertain if this is a clinically significant change from screening level for that individual participant. This determination, however, does not necessarily need to be made the first time an abnormal value is observed. The PI may repeat the laboratory test and/or request additional tests to verify the results of the original laboratory tests. The PI (or designee) will inform the MM of any unscheduled clinical laboratory testing, including but not limited to confirmatory testing of laboratory samples, with the exception that notification is not required for confirmatory testing for pregnancy, HCV, and HIV.

AV7909 Anthrax Vaccine
 IND 014451
 Protocol EBS.AVA.210, Version 3.0 (28 October 2019)

Investigational sites will be automatically notified of any Grade 3 or higher laboratory abnormalities. For any Grade 3 or higher laboratory result, the test will be repeated as soon as possible by the central lab using the same blood sample to confirm the result. The PI or designee must request the participant return to the clinic for an unscheduled visit for an assessment of clinical status. The decision to redraw laboratory tests will be made by the PI (with notification to the MM) and/or MM and will be based on the type and severity of the laboratory abnormality and the clinical status of the participant. Any Grade 3 or higher neutropenia or lymphopenia must be evaluated with an unscheduled repeat complete blood count (CBC) approximately 72 hours after the initial specimen was drawn.

If the original (retested sample) or repeat laboratory value is Grade 3 or higher or determined by the PI to be a clinically significant change from baseline for that participant, this will be considered an AE and will be recorded on the AE eCRF. Any other clinical laboratory abnormalities must also be reported as AEs if considered by the PI to be a clinically significant change from baseline. If an abnormal laboratory test result is a sign of a disease or syndrome, the disease or syndrome will be recorded as the AE/SAE and not the abnormal laboratory result. Clinical laboratory abnormalities may trigger individual participant or study halting rules (see [Section 7.1](#) and [Section 7.3](#)) and may require discontinuation of treatment.

Table 10: Screening/Safety Clinical Laboratory Tests


Hematology
 
 -Basophils -Eosinophils -Hematocrit -Hemoglobin -Lymphocytes -Monocytes -Neutrophils -Platelets -RBC count -WBC count 
Serum Chemistry
 
 -ALT -AST -Bilirubin -BUN -Creatinine -Glucose 	
Urinalysis
 
 -Appearance -Bilirubin -Color -Glucose -Ketones -Leukocyte esterase -Nitrite -Occult blood -pH -Protein -Specific gravity -Urobilinogen -Microscopic examination (only if protein, nitrite, leukocyte esterase, or occult blood results are positive) 
Additional Tests
 
 -FSH (only in postmenopausal women at Screening) -Serum/UPT (all WOCBP) -TSH 	
Viral Serology:
 
 -anti-HCV antibody -anti-HIV antibody -HBsAg 
Urine Drug Screen:
 
 -Amphetamines -Barbiturates -Benzodiazepines -Cannabinoids -Cocaine -Opioids - 
Autoantibodies
 
 -Rheumatoid factor (RF) -Antinuclear antibody (ANA) -Anti-double stranded deoxyribonucleic acid (dsDNA) antibodies
---	--	--

For the abbreviations used above refer to [Table 1](#).

AV7909 Anthrax Vaccine

IND 014451

Protocol EBS.AVA.210, Version 3.0 (28 October 2019)

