5. STUDY POPULATION

Participants will be recruited at up to five clinical research centers in the United States. At least 210 healthy adults meeting the eligibility criteria will be randomized 1:1:1 to one of the three IP groups: 70 in Group 1 (AV7909 + ciprofloxacin), 70 in Group 2 (AV7909 + doxycycline) and 70 in Group 3 (AV7909 alone). Groups 1 and 2 will each have two subgroups; the A subgroup (N=40) will undergo PK sessions while the B subgroup (N = 30) will not. Approximately the first 40 participants who are randomized into Groups 1 and 2 will be assigned to Treatment Group 1A or Group 2A, while those who are randomized into Groups 1 and 2 thereafter will be assigned to Groups 1B or 2B.

No waivers of inclusion and/or exclusion criteria will be permitted in the trial. The sites will be asked to implement procedures that will ensure a representative racial distribution among recruited participants and result in populations that are gender- and age-balanced (ie, between 40-60% male with 40-60% of participants in the two age ranges of 18-30 years of age and 31-45 years of age).

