5.1. Inclusion Criteria

Individuals must meet all of the following inclusion criteria for study participation:

1. Written informed consent obtained from the participant (dated, signed, and captured in the medical chart at the site).
2. A male or female, aged 18 to 45 years of age, inclusive, at the time of informed consent.
3. Healthy condition as established by medical history and clinical examination before entering into the study.
4. Have a body mass index (BMI) less than or equal to 35.0 kg/m² at the Screening visit.
5. Have adequate venous access for phlebotomies.
6. For a woman of childbearing potential (WOCBP), negative pregnancy test at Screening and pre-randomization on Day 1, not currently breastfeeding, and no intention to become pregnant during the study period through 12 months after last receipt of any investigational product (IP).

Every female participant is considered to be a WOCBP unless she is surgically sterile (ie, has had a hysterectomy, bilateral salpingectomy or bilateral oophorectomy) or postmenopausal [which is defined as >12 consecutive months without menses and a Screening FSH of >30 mIU/mL]. Adequate birth control (as defined here) must be initiated at least one month prior to randomization on Day 1 and used throughout the trial. Adequate birth control methods are sexual abstinence, intrauterine device/system (IUD/IUS), birth control pills, implantable or injectable contraceptives (eg, Norplant[®] or Depo-Provera[®]), removable birth control device (eg, NuvaRing[®] or Evra[®] patches) or double-barrier method of birth control (diaphragm in combination with contraceptive jelly or condoms in conjunction with contraceptive jelly, cream or foam), tubal ligation, or have a monogamous relationship with vasectomized partner who has been vasectomized for 6 months or more prior to the participant's trial entry.

AV7909 Anthrax Vaccine

IND 014451

Protocol EBS.AVA.210, Version 3.0 (28 October 2019)

Female participants randomized to Groups 1 or 2: be willing to add a double-barrier method, IUD, or abstinence as back-up forms of birth control since ciprofloxacin and doxycycline may decrease the effectiveness of birth control pills, implantable or injectable contraceptives.

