6. Confirm continued use of an adequate method of contraception and collect urine sample for pregnancy test for WOCBP (if positive, the participant must not be randomized; upon receipt of a confirmatory negative serum pregnant test result, the participant may be rescheduled for the Day 1 visit, providing the visit falls within the required window of the screening procedures).
7. Review for study eligibility against inclusion/exclusion criteria, to include a review of all safety and screening laboratory test results and status of ongoing AEs since the prior visit.

After the PI has confirmed that the participant meets all the inclusion criteria and none of the exclusion criteria, the participant will be randomized into one of the three IP groups.

1. Randomize eligible participants.
2. For participants who are WOCBP and randomized to Group 1 or 2: Re-educate participants that ciprofloxacin and doxycycline may decrease the effectiveness of birth control pills, implantable or injectable contraceptives. Instruct the participant to add a double-barrier method, IUD, or abstinence as back-up forms of birth control.
3. All randomized participants will have blood samples taken for TNA, TSH and autoantibodies.
4. Participants randomized to Group 2A will be instructed to return the same evening so that they can enter the first doxycycline PK session the following morning (See [Section 8.1.4](#)).
5. Participants randomized to Group 1A will be instructed to return to the site the evening of Day 3 so that they can enter the first ciprofloxacin PK session on Day 4 (See [Section 8.1.2](#)).

AV7909 Anthrax Vaccine

IND 014451

Protocol EBS.AVA.210, Version 3.0 (28 October 2019)

6. Participants randomized to Group 1B or 2B will be:

- provided their antibiotics [ciprofloxacin (Group 1B) or doxycycline (Group 2B)],
- provided instructions on the dosing regimen (twice daily at 12-hour intervals), beginning on the following day (Day 2) for those taking doxycycline (Group 2B) and beginning on Day 4 for those taking ciprofloxacin (Group 1B).
- informed about the dietary and lifestyle precautions required when taking each antibiotic (see [Section 5.3](#)).
- introduced to the e-diary for antibiotic compliance (see [Section 8.3.5.1](#)) and give instructions on how the e-diary should be used to record self-administered antibiotic doses.
- instructed to return on Day 8 to receive their first vaccination (See [Sections 8.1.3](#) and [Section 8.1.5](#)).

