#### 2.2.4.2 Clinical Laboratory Tests

All analytes to be tested during screening/safety/autoimmunity clinical laboratory tests are specified in Protocol EBS.AVA.210, [Table 10](#).

The following assessments will be performed at Screening only:

- Urine drug screen
- Serologic testing (HIV-1/HIV-2 antibodies, HBV surface antigen, and HCV antibody).
- Follicle-stimulating hormone (FSH) test in postmenopausal women.

Pregnancy testing will be performed at Screening, immediately following group assignment, before each vaccination, and at the Day 51 Final Study Visit or the EWV.

Blood and urine samples for safety clinical laboratory testing (hematology, serum chemistry, urinalysis) will be collected at Screening and Day 51 as well as at the EWV if the EWV occurs before Day 51.

Blood samples for TSH & autoantibody assessment of ANA, RF and anti-dsDNA will be taken at Day 1 after randomization, Day 51 or EWV or an unscheduled visit if the participant has received at least one dose of vaccine, and at the time of safety follow-up phone contact(s) if warranted from participant report(s) of a potential AESI. These samples will be shipped to the central laboratory and will be banked; testing for TSH and ANA, RF and anti-dsDNA autoantibodies will be performed only if medically indicated (as per PI's discretion).

All samples for testing will be sent to the central laboratory for analysis, except urine for pregnancy testing, which will be performed at the site and results documented in the eCRF.

Refer to Protocol EBS.AVA.210, [Section 8.3.2](#) for details on clinical laboratory tests.

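### Protocol Section 8.3.2 puts the Day 1 pregnancy test after group assignment and waives it within four days of a negative Screening serum test, contrary to inclusion criterion 6, Section 8.1.1.2 and the no-waiver rule

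*Protocol*

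**What the plan says.** Inclusion criterion 6 (Synopsis and Protocol Section 5.1) requires, for a woman of childbearing potential (WOCBP), a "negative pregnancy test at Screening and pre-randomization on Day 1". Section 8.1.1.2 puts the urine test among the steps done on Day 1 before randomisation; staff "collect urine sample for pregnancy test for WOCBP (if positive, the participant must not be randomized", with rescheduling possible after a negative serum test. Section 5 adds: "No waivers of inclusion and/or exclusion criteria will be permitted in the trial".

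Section 8.3.2 gives a different position for the test: "Pregnancy testing will be performed at Screening, immediately following group assignment, before each vaccination". It then exempts some women from it: "If group assignment occurs within four days of a negative Screening serum pregnancy test, a UPT does not have to be performed". The same section limits the consequences: "IP will not be administered to any participant who tests positive for pregnancy".

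SAP Section 2.2.4.2, part of the SAP's protocol summary, repeats the timing ("Pregnancy testing will be performed at Screening, immediately following group assignment") but not the four-day exemption.

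**The concern.** A site has two instructions for one eligibility test and no stated rule on which governs. Following Section 8.3.2, it could randomise a woman with no Day 1 result at all. She would not have met criterion 6, and Section 11.6 gives enrolment in violation of eligibility criteria as an example of a significant deviation.

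The practical stake is antibiotic exposure. Dosing starts on Day 2 in Group 2 and on Day 4 in Group 1, before either vaccination, so the pregnancy test that precedes the first vaccination comes too late to protect against it. Table 4 lists delayed fetal skeletal development for the tetracycline class, noting limited data for doxycycline, and requires discontinuation on pregnancy.

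**Working it through.** The plan gives no figure of its own here. The check compares the texts and then counts days.

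**1. The instructions side by side**

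| Source | When the Day 1 test is done | Four-day exemption |
|---|---|---|
| Inclusion 6 (Synopsis, 5.1) | before randomisation | none stated |
| Section 8.1.1.2 | before randomisation; a positive result bars it | none stated |
| Section 8.3.2 | after group assignment | yes |
| SAP 2.2.4.2 | after group assignment | not mentioned |
| Tables 5 to 9 | marked in the Day 1 column, order not stated | none stated |

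Section 8.3.2 cannot be read as describing a second test. The steps after randomisation in Section 8.1.1.2 contain no pregnancy test, and each schedule table marks a single Day 1 entry. The introductions to the schedules point to Section 8.1.1, while the pregnancy-test footnotes point to Section 8.3.2, so sites are sent to both.

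**2. Can the exemption apply?** Screening runs from Day -28 to Day -2. With no Day 0 (SAP 4.3), Day -k is k days before Day 1.

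- Permitted screening days: 28 - 2 + 1 = 27.
- Days within four days of Day 1: Days -4, -3 and -2, that is 3.

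**3. Which groups lose a test before their first product?**

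- Group 1A: urine test on Day 3, first dose on Day 4. The last test is 1 day old with or without the Day 1 test.
- Group 3: first product is the Day 8 vaccine, tested beforehand.
- Group 2A: no test at the Day 1 evening admission (Table 7 footnote g); the next is on Day 7, after dosing began on Day 2.
- Groups 1B and 2B: the next test is on Day 8, after dosing began on Day 4 and Day 2.

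In 1B, 2A and 2B the Day 1 test is therefore the only one scheduled between Screening and the first dose.

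**4. Age of the last negative test at first dose.** For a first dose on Day d, the age is d - 1 with the Day 1 test, and k + (d - 1) without it when the serum test was on Day -k.

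| Group | d | With Day 1 test | Without, k = 4, 3, 2 |
|---|---|---|---|
| 2A, 2B | 2 | 1 day | 5, 4, 3 days |
| 1B | 4 | 3 days | 7, 6, 5 days |

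The exemption adds k days, that is 2 to 4.

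**5. Doses before the next scheduled test**, at two per day and in the listed step order:

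- 1B: Days 4 to 7, 4 x 2 = 8.
- 2A: Days 2 to 6, 5 x 2 = 10, plus the Day 7 morning dose = 11.
- 2B: Days 2 to 7, 6 x 2 = 12.

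These doses precede that test under either wording. What the exemption takes away is the Day 1 test ahead of them.

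**The case against.** The best reply is that the stricter text already prevails. The exemption is permissive and forbids nothing. Sections 6.3.1 and 8.1.1.2 make the investigator confirm every inclusion criterion before randomisation, and Section 5 bars waivers. A careful site would test first. That lowers the chance of harm but does not remove the conflict: no precedence rule is stated, and the schedule footnotes refer sites to the section containing the exemption. The no-waiver rule does not mention pregnancy testing, so the absence of any exception in criterion 6 is read from its silence together with that rule.

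A second reply is that the timing phrase may loosely name the Day 1 visit, since the schedules head that column as group assignment. The wording specifies after assignment, which counts against this, but little turns on it: the timing half alone does not change what precedes dosing. A test just after assignment would still come before any product, and a positive result would stop dosing.

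Third, 3 of 27 is not a probability. Serum samples go to a central laboratory and results must be reviewed before randomisation. Turnaround is not given, so a Day -2 sample may not be back by Day 1. Section 5.4 also lets screening laboratory tests be delayed or repeated, so the serum date need not be the visit date. This stands.

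A reader might infer higher dose counts (9 in 1B, 12 in 2A, 13 in 2B) by adding the dose given at the visit of the next test. The numbered steps put the urine test before that dose each time (Sections 8.1.3.2, 8.1.4.4 and 8.1.5.2), so 8, 11 and 12 are right.

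**Conclusion.** The inconsistency is real and minor. It concerns eligibility and safety procedure. In three groups, a woman whose Screening serum test fell on Days -4 to -2 could begin antibiotic on a negative result 2 to 4 days older than criterion 6 intends. The day counts assume that dosing starts on the scheduled days and that the serum result is available by Day 1.

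The risk is small. A negative serum screen and at least one month of contraception are required. Product is withheld after a positive test, Section 9.4 withdraws a participant whose pregnancy is found before Day 2, and a negative urine test must precede each vaccination. The number of women affected cannot be derived, because the sex balance is only a recruitment request and the spread of screening dates is not given.

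A reader might infer that the exemption exposes women to 8 to 12 extra doses, or that it lets vaccination proceed untested. The documents support neither: the doses fall before the next test in any case, and the tests before vaccination are unaffected. Nor does it bear on any pharmacokinetic or immunogenicity result, or on power. The SAP sentence only summarises the protocol and directs no analysis.

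**What to change.** In Protocol Section 8.3.2, state that the test is done on Day 1 before randomisation, and delete the four-day exemption. Reword the summary sentence in SAP Section 2.2.4.2 to match, for consistency only.

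The cost is one protocol section and one SAP sentence. The only added procedure relative to Section 8.3.2 is a site urine test in WOCBP whose Screening serum test fell on Days -4 to -2, which criterion 6 already requires. If the sponsor regards a serum test two to four days old as sufficient, and the documents give no reason to reject that, writing the exemption into criterion 6 and Section 8.1.1.2 would also remove that part of the conflict. The timing wording would still need correcting. Deletion is simpler.
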